#### **Analysis Populations**

All statistical processing will be performed using SAS® unless otherwise stated. All subjects enrolled in the study that were dispensed and applied test article at least once will be included in the analysis of safety and efficacy and will be considered the intent-to-treat (ITT) population. Last-observation-carried-forward (LOCF) will be used to impute missing values for efficacy variables.

A subject will be included in the per-protocol (PP) efficacy analysis population if all of the following criteria are met:

- Subject meets the inclusion/exclusion criteria;
- Subject has not taken or applied any interfering concomitant medications
- Subject has completed Visit 4/Day 15 (± 2 days) and has missed no more than one Follow-Up Visit;
- Subject has been compliant with the dosing regimen (i.e., subject must take at least 80% of the expected doses up to and including the final visit).

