### 11.2 Concomitant Medications

The Investigator notifies the Medical Monitor regarding all medications taken by a subject during study participation, for treatment of Adverse Events or pre-existing conditions.

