### 12.5 Visit 4 (Day 9 + 1) Follow-Up to 7 Twice Daily Treatments

The study patient will return for a follow-up evaluation to the clinical site on Day 9 + 1. At this follow-up visit, the patient will undergo the following procedures and evaluations.

- Vital signs measurements including weight, temperature, resting blood pressure, heart rate, and respiratory rate
- Baseline laboratory tests (blood chemistries and hematology)
- Visual examination of the ulcer
- Scoring of the Ulcer(s) using the DUSS and DFI Wound n System
- Photo Documentation and Calculation of the Ulcer Area and Depth using the Aranz Medical SilhouetteTM System
- Collection of a sample from the ulcer for microbiological assessment
- Collection of Subject Home Treatment Log
- Collection of Investigational Product (IP)

Patients will be given a 7 day supply of non-abrasive bandage and written instructions on the proper care and hygiene to include keeping the ulcer clean and bandage dry until the Day 15 follow up visit. In addition, patients will be told to call if there is any worsening of the ulcer with regard to pain, infection, or swelling.

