### **5.3 Per-Protocol (PP) Population**

The PP Population will include all randomized subjects who receive all doses of investigational product as required by the protocol and have no major protocol violations. Major protocol violations will be reviewed and the subjects in the PP population will be identified prior to unblinding the study.

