## **8.2 Analysis of Efficacy Endpoints**

For each dose group, the proportion of subjects with a normal culture at the end of the MAD portion of the study will be compared to the proportion of subjects with a normal culture at the end of the MAD portion of the study for the combined placebo group using a Fisher's exact test. A subject with a normal culture at this time will be considered a success. Any subject with a missing value at the end of the MAD portion of the study will not be included in the analysis. A p-value less than 0.05 will be considered statistically significant and a p-value less than 0.0167, employing a Bonferroni correction for multiple comparisons, will be considered highly conclusive.

For continuous efficacy endpoints, data will be summarized descriptively at and a comparison using the Wilcoxon Rank Sum test between each of dose groups and the combined placebo group will be performed at each visit. For these endpoints, no imputation for missing values will be performed.

For categorical endpoints, a Fisher's exact test will be performed in a similar manner. Subjects missing a value for a secondary endpoint will be considered a failure (counted in the denominator) for that endpoint.

For all tests, a p-value less than 0.05 will be considered statistically significant and a p-value less than 0.0167, employing a Bonferroni correction for multiple comparisons, will be considered highly conclusive. Analysis for each secondary endpoint will be performed on the ITT population and the PP population.

Ulcer measurements and percentage of area reduction will be summarized descriptively by visit and statistical testing using a Wilcoxon Rank Sum test between each dose group and the combined placebo group. For all tests, a p-value less than 0.05 will be considered statistically significant. Analysis for each additional endpoint will be performed on the ITT population and the PP population.

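### SAP 8.2 scores end-of-MAD success without regard to antibiotics taken on study, and the per-protocol definitions disagree on whether such subjects stay in

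*SAP*

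**What the plan says.** **Success rule.** For culture at the end of the MAD portion, SAP 8.2 states: "A subject with a normal culture at this time will be considered a success". SAP 8.1 defines the DFI-component endpoints as absence of each sign. The only failure or exclusion rules in 8.2 concern missing data. For culture: "Any subject with a missing value at the end of the MAD portion of the study will not be included in the analysis". For categorical secondary endpoints: "Subjects missing a value for a secondary endpoint will be considered a failure (counted in the denominator) for that endpoint".

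**On-study medication.** Exclusion criterion 4 in Protocol 9.1.2 bars systemic or topical antibiotics in the seven days before entry. After entry, Protocol 11.2 says only: "The Investigator notifies the Medical Monitor regarding all medications taken by a subject during study participation". That section covers medication given for adverse events or pre-existing conditions. Protocol 12.7 has medication changes recorded at every visit. SAP 9.4 codes them to ATC level 4 and summarizes them descriptively, with no link to efficacy.

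**Analysis sets.** SAP 8.2 states: "Analysis for each secondary endpoint will be performed on the ITT population and the PP population". ITT is all randomized subjects (SAP 5.1, Protocol 16.2). PP is defined in three places:
- The protocol synopsis requires: "Subject has not taken or applied any interfering concomitant medications". It does not define which medications interfere.
- Protocol 16.2 lists seven major violations. None concerns concomitant medication.
- SAP 5.3 takes randomized subjects who "receive all doses of investigational product as required by the protocol and have no major protocol violations". It lists no violations and leaves them to review before unblinding.

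**The concern.** The entry exclusion accepts that recent antibiotics affect the ulcer's bacteriology. The same exposure after first dose has no consequence for scoring. If an antibiotic clears the culture or settles a DFI sign, the plan credits the assigned arm. On placebo this raises the comparator rate; on a dose it credits Nu-3 with clearance that another drug may have produced. The secondary objectives are to assess clinical and microbiological response and to support dose selection, and both need the endpoint to reflect Nu-3. The PP analysis would be the natural check on the ITT result, but whether it removes these subjects depends on which definition is followed.

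**Working it through.** **1. Trace one subject.** A randomized subject takes every dose, starts a non-study antibiotic before the end-of-MAD assessment (read here as the Day 9 visit), stays in the study and has a normal culture.

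| Rule | Result |
|---|---|
| SAP 5.1, ITT | Included |
| SAP 8.2, culture | Success |
| SAP 8.1 and 8.2, DFI sign absent | Success |
| Synopsis PP | Out, if antibiotics count as interfering |
| Protocol 16.2 PP | In: none of the seven violations applies |
| SAP 5.3 PP | In, unless the blinded review calls it a major violation |

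Two variants differ. If the subject leaves the study, violation 6 in 16.2 (not completing) removes the subject from PP. If no culture is taken, the subject drops out of the culture analysis and is not scored a success.

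**2. The plan's own figure.** SAP 8.2 sets a stricter threshold of 0.0167. For three dose-placebo comparisons, 0.05 / 3 = 0.0167, so it reproduces. No sample size or power is stated.

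**3. Group sizes.** SAP section 3 has three cohorts of 10, randomized 4:1, so 8 active and 2 placebo each. SAP section 4 pools placebo: 3 × 2 = 6. With the protocol's five cohorts, it is 5 × 2 = 10.

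**4. Effect of one reclassified subject.** Take n1 active, n0 placebo and s successes in all. Then P(x) = C(n1,x)·C(n0,s−x) / C(n1+n0,s). The two-sided Fisher p sums every P(x) no larger than the observed one. The outcome counts are assumed.

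- 5/8 v 0/6: (56 + 6) / 2002 = 0.031
- 5/8 v 1/6: (336 + 28 + 48 + 1) / 3003 = 0.138
- 6/8 v 0/6: (28 + 1) / 3003 = 0.0097, below 0.0167
- 6/8 v 1/6: (168 + 8 + 8 + 168) / 3432 = 0.103
- 8/8 v 1/6: 6 / 2002 = 0.003, still below 0.0167

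The shift can go the other way. 4/8 v 0/6 gives (70 + 15) / 1001 = 0.085. One antibiotic-treated active subject counted as a success makes it 5/8 v 0/6, p = 0.031.

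With 10 placebo subjects, 5/8 v 0/10 gives 56 / 8568 = 0.0065. Against 1/10 it is 798 / 18564 = 0.043, and against 2/10 it is 4608 / 31824 = 0.145.

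**5. Range for one scenario.** Assume true success of 80% on active and 10% on placebo, and that a share q of placebo non-responders take an antibiotic and become culture-normal, with none on active. The placebo rate becomes 0.10 + 0.90q. For q = 0, 0.10, 0.20 and 0.33 this is 0.10, 0.19, 0.28 and 0.397. Exact power at 0.05 is then:

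| Active rate, group sizes | q = 0 | 0.10 | 0.20 | 0.33 |
|---|---|---|---|---|
| 80%, 8 v 6 | 70% | 51% | 35% | 19% |
| 80%, 8 v 10 | 84% | 65% | 48% | 29% |
| 70%, 8 v 6 | 52% | 34% | 21% | 11% |
| 90%, 8 v 6 | 86% | 71% | 54% | 34% |

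Every rate here is an assumption. The table shows sensitivity, not an expected loss.

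**The case against.** **Counting outcomes whatever else was taken is a legitimate ITT choice.** True, but the SAP does not present it as a choice, and it answers a different question from Nu-3 activity. It belongs beside the main analysis, labelled as such.

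**Few subjects may be affected.** The window to the test is about eight days. Protocol 9.2 requires withdrawal for an illness that the investigator thinks may significantly affect the subject or study. Blinded review could remove others from PP, and Listings 16.2.7 and 16.2.8 make them identifiable. This narrows the problem but does not set a scoring rule for those who stay and are cultured.

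**5/8 v 0/6 is a borderline example.** Agreed. It is the smallest significant result against 0/6, and 8/8 survives one reclassification. The figures show fragility in small groups, not expected bias.

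Three stronger readings are tempting and are not supported:

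- *The rule biases results against Nu-3.* This needs more antibiotic use on placebo, and no rate is given. Protocol section 6 reports that 2% Nu-3 irritated abraded skin more than saline, so local reactions, and any treatment they prompt, need not be commoner on placebo.
- *Such a subject is a success in both ITT and PP.* The synopsis criterion would remove the subject if antibiotics count as interfering, and no document says which PP definition prevails. For PP the finding is a conflict between definitions.
- *The protocol plans for antibiotic treatment before the tested visit.* Protocol 12.5 says "patients will be told to call if there is any worsening of the ulcer with regard to pain, infection, or swelling", but that instruction is given at Visit 4 for the interval to Day 15. It cannot produce treatment before the Day 9 assessment. The remark on more aggressive therapy (Potential Risks) is in the appended three-cohort version, whose section 4.4 lets subjects continue only medication for conditions unrelated to the ulcer.

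**Conclusion.** The gap is real for ITT. Following SAP 8.2 as written, an antibiotic-treated subject who remains in the study with a normal culture or an absent sign is a success, and this contaminates the estimate in whichever arm it occurs. The direction is unknown; it is toward no effect only if use is commoner on placebo. For PP, the synopsis disagrees with Protocol 16.2 and SAP 5.3, and the passages must be reconciled.

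The size depends on how many subjects are affected, which the documents do not indicate. With 8 per dose and 6 pooled placebo, a single subject can move a borderline result across 0.05 in either direction; a clear result such as 8/8 withstands it. Efficacy is a secondary objective in a pilot with no sample size calculation, so this should be fixed but does not threaten the primary safety objective.

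**What to change.** - **SAP 8.2, culture and DFI-sign endpoints:** score a subject as a non-success at an assessment if a systemic antibiotic, or a topical antimicrobial on the ulcer other than test product, was taken between first dose and that assessment. As a sensitivity analysis, show the result regardless of antibiotic use.
- **Continuous endpoints:** show results with and without such subjects.
- **PP:** carry the synopsis criterion on interfering medication into Protocol 16.2 and SAP 5.3, and define it to include these antibacterials, so that all three definitions agree.

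This changes scoring only, not whether or when antibiotics are given. The cost is SAP and protocol wording plus one derived flag from medication data already collected and coded. Observed success rates may be slightly lower, and a few subjects treated for unrelated infections will be scored as non-successes; the sensitivity analysis shows how much that matters. The change must precede database lock to count as a priori under SAP section 4.

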#### 9.1.1 **Inclusion Criteria**

- 1. Men and women between the ages of 18 and 85.
- 2. Voluntary written consent, given before performance of any clinical investigation-related procedure not part of standard medical care, and with the understanding that consent may be withdrawn at any time without prejudice to future medical care.
- 3. Non-hospitalized ambulatory subjects suffering from Diabetes mellitus, Type I or II
- 4. Diabetic foot ulcer(s) with a DUSS Score of 0 to 3
- 5. Ulcerated area(s) of not more than two (2) ulcers between 0.5 to 6 cm^2
- 6. Any female of child bearing age must consent to use medically acceptable birth control for the duration of the study
- 7. Female subjects must meet at least one of the following additional criteria:
  - d. Surgically sterile with bilateral tubal ligation or hysterectomy.
  - e. Post-menopausal for at least one year.
  - f. If of child-bearing potential, practicing an acceptable method of birth control for the duration of the clinical investigation as judged by the Investigator, such as condoms, foams, jellies, diaphragm, intrauterine device or abstinence.
- 8. Subjects willing to undergo pre-and post-clinical investigation blood collection, physical exams and laboratory investigations..

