#### Diabetic Foot Ulcer Wound Infection Score

Parameter	Wound Infection Score						
rarameter	0	1	2	3			
Purulent discharge	Absent			Present			
Nonpurulant drainage (serious, sanguinous)	Absent	Mild					
Erythema	None	Mild pink, barely perceptible	Moderate pale red, defined edges	Severe red to dark red			
Induration	None	Mild	Moderate	Severe			
Tenderness (sign)	None	Mild	Moderate	Severe			
Pain (symptoms)	None	Mild	Moderate	Severe			
Local Warmth (relative to uninfected contralateral foot)	Same	Mildly increased	Moderately increased	Severely increased			

An improvement in the DFI Wound Score will be used to indicate a clinical improvement of the wound and a change in the DUSS Score wound be used to indicate the healing of a small ulceration.

Microbiological Response Evaluations:

This assessment will be conducted on samples collected by the investigator on Visit 2, Visit 4, Visit 5, and Visit 6.of the study which will be cultured to determine: microbial load and identity of the infected pathogens or wound flora. The microbiological response will be determined by a comparison of the results pre- and post-treatment.

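### SAP 8.2 has no value for a fully closed ulcer, so a subject whose ulcers have all healed, leaving no specimen or tracing, is dropped from the culture and wound-size tests because of that outcome

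*SAP*

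**What the plan says.** SAP 8.2 (Analysis of Efficacy Endpoints) has three missing-value rules.

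- **Culture.** "A subject with a normal culture at this time will be considered a success", the time being the end of the MAD portion. A subject without a culture then is left out: "Any subject with a missing value at the end of the MAD portion of the study will not be included in the analysis".
- **Continuous endpoints.** "For these endpoints, no imputation for missing values will be performed". The later paragraph on ulcer measurements and percentage area reduction adds no rule of its own.
- **Other categorical endpoints.** "Subjects missing a value for a secondary endpoint will be considered a failure (counted in the denominator) for that endpoint".

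The synopsis of the current protocol (Analysis Populations) has a different rule: "Last-observation-carried-forward (LOCF) will be used to impute missing values for efficacy variables".

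On how the data arise, protocol 12.5 lists for Visit 4 (Day 9) "Collection of a sample from the ulcer for microbiological assessment". Appendix A of the current protocol obtains area, depth and volume by having the operator outline the ulcer's edge on an image. SAP 8.1 analyses total wound size per subject. Protocol 9.1.1 admits "Ulcerated area(s) of not more than two (2) ulcers between 0.5 to 6 cm" (squared). Neither document gives a closed ulcer a zero area, a 100% reduction or a culture category, and normal culture is not defined.

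**The concern.** The rules treat a missing value as an absence of information. For a closed ulcer it is the reverse: the visit was attended, the ulcer was seen, and there was nothing to swab or trace. Whether the subject enters the comparison then depends on the outcome being compared. Culture success is understated in the arm where this happens, and the largest area reductions leave the Wilcoxon tests unless someone enters a zero.

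The other rules in the documents do not help. Counting missing as failure would score a healed subject as a failure. Carrying the last observation forward would give a healed subject the last open-ulcer value.

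**Working it through.** **Inputs.** SAP section 3: three cohorts of 10, randomised 4:1, so 8 on Nu-3 and 2 on placebo in each. SAP section 4: placebo pooled, so 3 × 2 = 6; the current protocol's five cohorts would give 5 × 2 = 10. Tests are two-sided. Closure and response rates are not in the documents, so every value below is an assumption.

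**The plan's own figure.** 0.05/3 = 0.01667, which reproduces the SAP's stricter threshold of 0.0167 for three dose groups.

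**Which visit.** MAD dosing starts on Day 2 and lasts 7 days, so the culture test falls at Visit 4, nominally Day 9. SAP 8.2 compares continuous endpoints at each visit, so closures by Day 15 can also matter there.

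**Bias in one arm.** Counting closure as success, the success rate is c + (1−c)p. Excluding closed ulcers estimates p. The difference is c + (1−c)p − p = c(1−p).

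| c | p = 0.7 | p = 0.5 | p = 0.3 |
|---|---|---|---|
| 0% | 0 | 0 | 0 |
| 5% | 1.5 points | 2.5 | 3.5 |
| 10% | 3 | 5 | 7 |
| 20% | 6 | 10 | 14 |
| 30% | 9 | 15 | 21 |

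One closure among 8 removes 1/8 = 12.5% of a dose group.

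**Bias in the comparison.** Excluding closures understates the Nu-3 minus placebo difference by c_N(1−p_N) − c_P(1−p_P), where N is Nu-3 and P placebo. If this is negative, excluding them overstates the difference.

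**Culture illustration, 8 v 6.** Nu-3: 2 closed, 4 open and normal, 2 open and abnormal. Placebo: 0 of 6 normal. Fisher's exact test:

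- closed excluded: 4/6 v 0/6, p = 0.061
- closed as success: 6/8 v 0/6, p = 0.0097
- closed as failure: 4/8 v 0/6, p = 0.085

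With 1 closed instead (5 normal, 2 abnormal), exclusion gives 5/7 v 0/6, p = 0.021, against the same 0.0097.

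**Area illustration, 8 v 6.** Invented reductions: 20, 30, 40, 50, 60, 100, 100, 100% on Nu-3 and 0, 5, 10, 15, 25, 35% on placebo. With closures at 100%, the Nu-3 median is 55% and exact Wilcoxon p = 0.0047. With the three closures dropped, the median is 40% and p = 0.030. The estimate moves, but both p-values are below 0.05, the only threshold in the ulcer-measurement paragraph.

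**Power, full enumeration, 60% v 20% normal among open ulcers, alpha 0.05.**

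| Sizes | Closure, Nu-3 v placebo | Understatement of difference | Closed = success | Closed dropped |
|---|---|---|---|---|
| 8 v 10 | 30% v 5% | 12 − 4 = 8 points | 0.403 | 0.249 |
| 8 v 10 | 10% v 5% | 4 − 4 = 0 | 0.283 | 0.290 |
| 8 v 10 | 5% v 5% | 2 − 4 = −2 | 0.258 | 0.299 |
| 8 v 10 | 10% v 10% | 4 − 8 = −4 | 0.221 | 0.282 |
| 8 v 6 | 5% v 5% | 2 − 4 = −2 | 0.177 | 0.175 |

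Counting closures as success raises power clearly only when closure is much more common on Nu-3. At similar rates it makes little difference or lowers power.

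**The case against.** The premise is an inference. No passage says that a closed ulcer yields a missing value. The Schedule of Events plans a swab at every visit, a site might swab the closed skin and report no growth, and zero is the natural entry for the area of a closed wound. This stands, and it makes the point conditional. It does not remove it, because nothing tells sites to do either.

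Full closure may also be rare. The culture test needs every ulcer of a subject with chronic disease to be closed by about Day 9. A subject with one of two ulcers closed still has a total wound size under SAP 8.1 and an ulcer left to swab. Both points stand.

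A reader might infer from "a change in the DUSS Score wound be used to indicate the healing of a small ulceration" that the sponsor expected complete closure. The text does not support that. It comes from a superseded protocol version bound in the same file, and DUSS scores pulses, probing to bone, location, and single or multiple ulcers. The change that healing most directly produces is from multiple to single, which leaves an ulcer to measure.

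Counting an uncultured ulcer as a culture success makes the endpoint partly a healing endpoint. That is a fair criticism, and it is why the fix asks for a separate row and a sensitivity analysis.

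Finally, the primary objective is safety, this is a pilot with no sample size calculation, and individual closures could be seen in listings 16.2.8, 16.2.11 and 16.2.15. This limits the severity. Listings do not correct the tabulated proportions or p-values.

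**Conclusion.** The point holds as a conditional gap. Where complete closure leaves no specimen or tracing, SAP 8.2 removes the subject because of a best-case outcome, understating culture success in that arm by c(1−p) and taking the largest area reductions out of the Wilcoxon tests unless a zero is entered. With no closures the effect is nil. The documents give no closure rate, so the true size is unknown.

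Two stronger readings are tempting and not supported. One is that the rule works against Nu-3: it does so only when c_N(1−p_N) exceeds c_P(1−p_P). The other is that it costs power: that depends on the assumed closure rates and can reverse. The case rests on exclusion driven by outcome, not on power. This is a cheap improvement to secondary analyses.

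**What to change.** Before database lock, add to SAP 8.2:

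- **Wound size.** When the investigator documents complete closure at an attended visit, area, perimeter, maximum and mean depth, volume, length and width are 0 and area reduction is 100%.
- **Culture.** Closed with no specimen is shown as its own row, counted as success in the main comparison, and excluded in a sensitivity analysis.
- **Missing values.** The existing rules apply only to values that are truly missing, and SAP 8.2 replaces the last-observation-carried-forward rule in the protocol synopsis.

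The cost is a few sentences in the SAP and a tick box for closure without specimen in the electronic source; the ulcer is already examined visually at every visit. The downside is that closure counts as microbiological success without a culture, which the separate row and the sensitivity analysis expose. Timing matters because SAP section 4 treats any analysis performed after database lock as post hoc.

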## 3. STUDY OVERVIEW

This is a phase 1/2a prospective, multi-center, blinded, randomized, dose escalation study. This study will be conducted at four investigational sites. Subjects with diabetic chronic foot ulcer(s) and a Diabetic Ulcer Severity Score (DUSS) of 0 to 3, ulcerated area(s) of not more than two ulcers between 0.5 and 6 cm^2, and no underlying DUSS Probing to Bone='Yes' are eligible to be enrolled into the study.

Doses of Nu-3 will be escalated in three planned sequential cohorts with 10 subjects in each cohort. Randomization will be 4:1 active to placebo in each cohort. The dose levels in each cohort are:

- Cohort 1 – 0.1% solution of Nu-3 in 0.9% saline with vehicle
- Cohort 2 – 1% solution of Nu-3 in 0.9% saline with vehicle
- Cohort 3 – 2% solution of Nu-3 in 0.9% saline with vehicle

Each cohort has placebo defined as 0.9% saline with vehicle. Dosing will be twice daily for 7 consecutive days.

Subjects will have scheduled study visits as follows:

- Screening (Day -7 to -4 hours)
- Single dose visit (Day 1)

- Safety review and multiple dose visit (Day 2)
- Safety review visit (Day 9  $\pm$ 1 day)
- Final Visit (Day 15  $\pm$ 2 days)

At the conclusion of each cohort, a Safety Review Committee will review the safety data and determined if it is safe to proceed to the next cohort. The committee includes, but is not limited to the Sponsor's designated Medical Monitor, the Medical Director of the CRO, and the Medical Director of Lakewood Amedex. Additional members can be added as the sponsor deemed appropriate.

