#### **4. GENERAL ANALYSIS CONSIDERATIONS**

The statistical analyses will be reported using summary tables and data listings. For all efficacy parameters, a comparison will be made of each active treatment group versus placebo using the appropriate statistical test. Unless otherwise indicated, all statistical tests will be two-sided and differences will be considered statistically significant if the associated p-value is less than 0.05. Continuous variables will be summarized with means, standard deviations (SD), medians, minimums, and maximums. Categorical variables will be summarized by counts and by percentage of subjects in corresponding categories. All data will be summarized by dose group (cohort), with all placebo subjects combined into one placebo arm.

Individual subject data obtained from the electronic data capture system, study lab, and any derived data will be presented by cohort for each subject in data listings.

The analyses described in this plan are considered *a priori*, in that they have been defined prior to database lock for individual subjects. Any analyses performed subsequent to database lock will be considered post-hoc and exploratory. Post-hoc analyses will be identified in the CSR.

All analyses and tabulations will be performed using SAS® Version 9.4 or higher on a Windows platform. Tables and listings will be presented in PDF format. Upon completion, all SAS® programs will be validated by an independent programmer. In addition, all program output will undergo a senior level statistical review. The validation process will be used to confirm that statistically valid methods have been implemented and that all data manipulations and calculations are accurate. Checks will be made to ensure accuracy, consistency with this plan, consistency within tables, and consistency between tables and corresponding data listings. Upon completion of validation and quality review procedures, all documentation will be collected and filed by the project statistician or designee.

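### SAP 8.2 uses a flat Bonferroni cut and leaves the Wilcoxon p-value method open; Holm with stated exact p-values keeps the 5% bound, with a gain that depends on endpoint and effect size

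*SAP*

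**What the plan says.** SAP section 3: "Doses of Nu-3 will be escalated in three planned sequential cohorts with 10 subjects in each cohort", and "Randomization will be 4:1 active to placebo in each cohort". SAP section 4: "All data will be summarized by dose group (cohort), with all placebo subjects combined into one placebo arm". The same section sets the general rule that "all statistical tests will be two-sided and differences will be considered statistically significant if the associated p-value is less than 0.05", and names SAS 9.4 or higher without naming an exact option.

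SAP section 8.2 then sets the tests:

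- Normal culture: each dose is compared with the proportion "for the combined placebo group using a Fisher's exact test". The other categorical endpoints are also tested with Fisher's exact test.
- Continuous endpoints: "a comparison using the Wilcoxon Rank Sum test between each of dose groups and the combined placebo group will be performed at each visit". Exact or asymptotic is not stated, and missing values are not imputed.
- Stricter tier: "a p-value less than 0.0167, employing a Bonferroni correction for multiple comparisons, will be considered highly conclusive". This sentence appears for culture and again in the general paragraph that follows the continuous and categorical endpoints.
- Ulcer measurements have their own paragraph: "Ulcer measurements and percentage of area reduction will be summarized descriptively by visit and statistical testing using a Wilcoxon Rank Sum test". That paragraph gives only the 0.05 cut.

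SAP section 10 reports no sample size calculation, and neither document gives an effect size, SD, response rate or power.

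**The concern.** The stricter tier is the only multiplicity adjustment in the efficacy plan. Two features make it less useful than it could be.

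First, every dose is held to 0.05/3 regardless of how many other doses have already passed. A step-down rule with the same family-wise bound would ask less of the second and third doses.

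Second, with groups this small, different ways of computing the Wilcoxon p-value give materially different tail probabilities. The SAP presents these analyses as fixed before database lock. Yet whether a result earns the stricter label can turn on a programming choice that it does not make.

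What is at stake is power, and a reproducible label, for the secondary aim of supporting a dose range with eight subjects per dose.

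**Working it through.** **Inputs.** From the SAP: three cohorts of 10 at 4:1, so 8 active and 2 placebo per cohort; pooled placebo 3 × 2 = 6; each comparison at most 8 v 6 with a shared control; two-sided 0.05; stricter cut 0.0167. Assumed, because the documents give none: normal shifts of 0.5 to 3 SD; culture rates of 5–30% on placebo and 40–90% on active. The main protocol (sections 8.3 and 16.5) describes five cohorts and prints a different cut; the figures here follow the SAP.

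**The plan's own figure.** 0.05/3 = 0.01667, which reproduces 0.0167.

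**Holm.** Order the three p-values. The smallest must be below 0.05/3 = 0.0167; if it passes, the next must be below 0.05/2 = 0.025; if that passes, the last must be below 0.05. The first step is the SAP's own cut and later cuts are wider, so nothing that Bonferroni rejects is lost. Example: 0.010, 0.020 and 0.049 give one rejection under the flat rule and three under Holm.

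**Wilcoxon at 8 v 6, untied.** There are C(14,6) = 3003 allocations. The rank sum of the group of 6 has mean 6 × 15/2 = 45 and variance 6 × 8 × 15/12 = 60 (SD 7.746). At rank sum 26:

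- exact: 19 allocations have sum 26 or less, so p = 2 × 19/3003 = 0.0127
- normal, no continuity correction: z = 19/7.746 = 2.45, p = 0.0142
- normal, continuity-corrected: z = 18.5/7.746 = 2.39, p = 0.0169

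The first two pass 0.0167 and the third does not. The corrected version rejects only at 25 or less, a true size of 2 × 12/3003 = 0.8% instead of 1.27%.

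At the 0.05 cut there is no such difference. Rank sum 29 gives 0.0426 exact and 0.0454 corrected (both reject); 30 gives 0.0593 and 0.0612 (neither does).

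**Power per dose.** Simulation, 100,000 runs, untied normal data, all three doses shifted equally:

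| Shift | Flat 0.0167, continuity-corrected p | Holm, exact p | Gain (points) |
|---|---|---|---|
| 0.5 SD | 3.1% | 5.3% | +2 |
| 1.0 SD | 13.6% | 22.2% | +9 |
| 1.5 SD | 36.6% | 53.4% | +17 |
| 1.8 SD | 54.1% | 72.4% | +18 |
| 2.0 SD | 65.3% | 82.4% | +17 |
| 2.5 SD | 86.7% | 96.1% | +9 |
| 3.0 SD | 96.5% | 99.5% | +3 |

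At 1.5 SD, exact p alone takes 36.6% to 44.5% (+8) and Holm takes 44.5% to 53.4% (+9).

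**Sensitivity at 1.5 SD.**

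- Baseline without continuity correction: it has the same rejection cut as the exact test, so only Holm's +9 remains.
- Only one dose works: about +7 to +8, all from exact p and none from Holm.
- Integer scores with ties, all doses active (8,000 runs): about +13 to +14 if the SD is 2 to 3 points, about +11 if 1 point, about 0 if 0.5 point. In the last case Holm adds about 8 points and the exact p-value takes back about as much.

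**Culture (Fisher, already exact).** Holm adds 0 to 7 points over the rates tried; for 10% v 80%, 49.9% becomes 55.2%.

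**Attained family-wise error over the three doses.** Global null: 2.1% to 3.4%. Two active doses (1.5 to 5 SD) and one null: 0.8% to between 2.8% and 4.3%.

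**The case against.** A reader might infer from the 1.5 and 2 SD rows that the change is worth about 17 points per dose. The documents do not support that as a general figure. It needs effects of that size, all doses active, untied data and a continuity-corrected p-value, and the SAP states none of these. The endpoints that clearly carry the 0.0167 cut are culture and categorical items, already tested exactly, and the DUSS and DFI changes, which are integer scores with ties. The ulcer measurements, closest to untied, have only the 0.05 cut in their own paragraph, where the exact and continuity-corrected tests agree at 8 v 6.

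Nor is the exact p-value always the more powerful. For a two-valued change score with assumed improvement rates of 10% and 70%, power at 0.0167 falls from 38.9% with the tie-corrected, continuity-corrected normal p to 31.9% with the exact p. This stands: stating exact fixes the rule, but for heavily tied DUSS changes it can cost power.

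It can also be said that the SAP has two deliberate tiers, and under Holm the last dose faces the same 0.05 as the lower tier. That is a fair preference; reporting the raw p-value beside the adjusted one keeps the information.

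Finally, efficacy is secondary, the study is a pilot, and no SAP decision rule depends on the stricter label. This limits the importance of the point but does not remove it.

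**Conclusion.** The point holds as an efficiency improvement and a gap in specification. Flat Bonferroni is valid; Holm is better on the same p-values under the same 5% bound. The unspecified Wilcoxon method can change the label on identical untied data at 8 v 6, and that finding needs no assumed effect size.

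The power gain is conditional, and Holm is not free of cost in error terms: the 5% bound is the same, but the attained error moves closer to it. A reader might also infer that the efficacy claims would then be error-controlled overall. They would not: either rule covers three doses within one endpoint, time point and population, and leaves the several endpoints, the visits and the ITT and per-protocol analyses unadjusted.

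All power figures rest on assumed effects and on full cohorts; missing values would make the groups smaller than 8 v 6.

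**What to change.** In SAP section 8.2, wherever the 0.0167 rule applies:

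1. Replace the flat cut with Holm's step-down across the three dose-versus-placebo comparisons (0.05/3, 0.05/2, 0.05), within a named endpoint, time point and population. Report raw and Holm-adjusted p-values side by side.
2. State that Wilcoxon rank sum p-values are exact, two-sided and conditional on the observed ties. Use the same statement for the ulcer measurements so that one method serves throughout.
3. Say that the adjustment does not extend across endpoints, visits or populations.

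The cost is a few sentences and one program option before database lock, with no new data. The price in error terms is the rise in attained family-wise error shown above, still below 5%, and possibly some power on very heavily tied scores.
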